#### 1.4 Preliminary Data

Preliminary data in 10 studies supports the use of high frequency TENS (>100 Hz) for pain relief post-Cesarean. Alves Lima et al (2014) compared the effectiveness of high frequency (100 Hz) and low frequency (4 Hz) TENS for pain relief post-Cesarean. High frequency TENS was more effective to reduce pain than low frequency TENS ( $p<0.05$ ). A review by Vance et al (2014) confirmed the superior effectiveness of high frequency TENS compared to low frequency TENS for acute post-surgical pain and for patients taking opioid medications. Since women after Cesarean Section in this study will have acute post-surgical pain and be prescribed opioid medications, high frequency TENS was selected for the study intervention.

Literature support exists for both continuous and 30-minute interval settings for the delivery of TENS after Cesarean Section for 24, 48 and 72 hours post-operatively. Six out of the 10 preliminary studies utilized continuous TENS rather than 30-minute intervals in order to increase the total dosage of electrical stimulation intervention delivered to patients after surgery over the inpatient hospital stay. While both continuous and interval settings of TENS have been shown to be therapeutically effective to reduce pain, differences in subjects' perception of comfort with TENS may exist between continuous and interval settings, with continuous being rated as more comfortable. This protocol has selected continuous TENS because: 1) continuous TENS has been shown to be as effective as 30-minute TENS intervals, and 2) continuous TENS may allow participants to receive a lower intensity electrical stimulation over a longer duration, thereby providing a comparable dosage of electrical stimulation over time when compared to a higher intensity over a shorter period of time (30-minutes). This distinction is important because women in this study will be experiencing acute post-surgical pain after Cesarean Section delivery. The research team has selected continuous TENS setting at a subject-selected intensity that is comfortable in order to afford participants the same therapeutic benefit as 30-minute interval TENS, which would be set at a higher sensory threshold intensity and which may not be as comfortable for participants in order to be therapeutically effective.

Souza Alves 2015 published results of a clinical randomized study in which 30 women received TENS for 30 minutes post-CS and 30 post-CS women in a control group did not. For the intervention group, there was a statistically significant decrease in the reported pain intensity before and after electrical stimulation ( $p=0.001$ ). (Figure 1) There was not a significant difference between the pain intensity between control and intervention.

[figure not shown]

Figure 1. Medians and their quartiles before and after intervention.  
VAS = visual analog scale; intervention group = Before (Md=45.00, 1st quartile=36.00 and 3rd quartile=56.00); After (Md=15.50, 1st quartile=5.75 and 3rd quartile=27.50); Wilcoxon test. \*Statistical significance ( $p=0.001$ ).

Karakaya et al (2012) published results of a clinical randomized study in which women received TENS for 30-minute intervals, combined with physiotherapy in the postpartum room ( $n=26$ ), or usual postpartum care ( $n=24$ ). There was a statistically significant difference between the intervention group and the control group in pain intensity at both POD-1 and POD-2.

Table 1

	Intervention Group	Control Group	t	p value
POD-0	0.612 +/- 0.268	0.668 +/- 0.315	-0.689	0.494
POD-1	0.362 +/- 0.173	0.532 +/- 0.280	-2.612	0.012
POD-2	0.352 +/- 0.194	0.514 +/- 0.280	-2.391	0.021

Version Number: 5

Protocol Number: Pro2018001008

PI Name: [name]

Protocol Title: TENS after Cesarean Delivery

6

RESERVED FOR IRB STAMP

DO NOT MODIFY THIS SPACE

IRB ID: Pro2018001008

IRB Form Version: 01/2018 Approval Date: 7/19/2022

Expiration Date: 7/18/2023

There are many research publications that suggest that TENS is an effective pain relief method post-Cesarean section. However, there has not been any published data examining whether TENS throughout delivery hospitalization when opioid use is the highest can provide an alternative to prescribing opioids to post-CS patients.

### **1.5 Sample Size Justification**

This is a pilot feasibility study to evaluate effectiveness and acceptability in our patient population of TENS use throughout delivery hospitalization. We aim to have 20 participants total: 5 in control and 5 in intervention without history of opioid addiction, and 5 in control and 5 in intervention with history of opioid addiction/misuse. This sample size is comparable to other shorter term pilot studies. This pilot study will serve as the basis for larger trials in the future, with larger sample size powered to demonstrate reduction in pain scores. We anticipate recruitment for this trial will take approximately 6-9 months.

### **1.6 Study Variables**

#### **A. Independent Variables, Interventions, or Predictor Variables**

The intervention for this study will be the application and use of Transcutaneous Electrical Nerve Stimulation (TENS) unit. The TENS unit uses low-voltage electric currents to temporarily block pain receptors and is currently used to treat bone, muscle, and joint pain. The TENS unit is not part of standard inpatient postpartum care.

#### **B. Dependent Variables or Outcome Measures**

Dependent variables will include: pain ratings and subjective incisional complaints, number and type of pain medications used, patient satisfaction with pain control, time to first bowel movement, level of sedation and time to OOB. Secondary measures will include pain surveys at discharge, and at 6 weeks postoperatively.

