#### **A. Objectives**

- To determine if the addition of TENS therapy to the pain management of women post-C-Section leads to less opioid medication use.
- To evaluate the efficacy of TENS therapy as a means of alternative pain relief for women post-C-section (CS) and for postpartum women with a history of opioid use.

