In addition to toxicity, prescribing opioids to new mothers, whether breastfeeding or not, bears a risk of misuse and addiction. The Substance Abuse and Mental Health Services Administration reports an annual average of approximately 21,000 pregnant women who have misused opioids in the past month. Access and adherence to opioid use disorder treatment remains a significant hurdle for new mothers. The accumulation of these risks underscore the clinical significance of finding alternative pain relief methods.

Non-pharmacological interventions for pain management, such as Transcutaneous Electrical Nerve Stimulation (TENS), have been shown to reduce painful incisional symptoms and reduce intake of opioid pain medications in women after CS (Jaafarpour et al, 2008; Kerai et al, 2011; Karakaya et al, 2011). TENS is a low-cost, effective intervention that can be applied safely by physical therapists, nurses and physicians on the inpatient floor. Studies have demonstrated that patients can be educated on self-administration of TENS. This pilot project proposes the use of TENS on the inpatient postpartum floor starting at 8 hours post-operatively and continuing until discharge home. It is hypothesized that women who utilize TENS after CS will consume less opioid medication during the inpatient stay compared to women who do not utilize TENS after CS.

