Following cesarean delivery, subjects will be re-approached in the Postpartum Unit at Robert Wood Johnson University Hospital by study staff. The TENS device will be again reviewed, and provided to the patient, with review of instructions for use. The patients in the intervention group will be educated on the proper way to utilize the TENS unit. They will apply the patches of the TENS unit above and below the C-section site. Specifically, the electrode patches will be placed above the abdominal bandages post-operatively and replaced above the abdominal bandages after the dressing change on post-operative day 1. Starting 8 hours after C-Section, the TENS unit will be turned on to a comfortable intensity as determined by the patient and will remain on until the patient is discharged, to be removed for toileting and showering and at the patient's discretion. Once the TENS unit is applied and turned on, the patient will not have to do anything else to maintain the therapy. Study staff will provide a record for documentation of time on/off for the unit. Additionally, a member of the study staff will check on the device daily to ensure proper maintenance. On the day of discharge, study staff will collect the device, and conduct a short survey about pain scores. They will then review pain scores, pain medication usage and other secondary outcomes in the patient's chart. Finally, pain will be reassessed at the subject's outpatient postpartum visits by study staff. The subjects will complete a measure of perceived physical disability at the outpatient postpartum visit.

**DATA COLLECTION.** Our research team members will collect the following data points from the patient's inpatient medical record: pain scale scores, medication requests/prescriptions (including name, type, and amount), time to first bowel movement, subjective incision site complaints, and time to OOB. Participants will complete a survey before discharge which will solicit additional information about the postpartum recovery experience with or without TENS therapy. (Survey is submitted with this protocol as Appendix A.) Participants will complete a survey at the 6-week postpartum visit on perceived difficulties because of health (The survey, WHODAS 2.0, is submitted with the protocol as Appendix B).

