#### **D. Subject Screening**

- Physicians that have a direct treatment relationship with the patient will inform the patient about the study and invite them to enroll. [name] will confirm eligibility thereafter.

- **Inclusion Criteria**

- Women aged between 18 and 45 years
- Understand and be able to follow written and oral instructions in English
- Provide written informed consent
- History of prior opioid addiction for half of the patients. (Opioid use will be obstetric patients on narcotic replacement with methadone or subutex.)

- **Exclusion Criteria**

History of cardiac arrhythmia or pacemaker usage

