TENS and Opioid Use After Cesarean Delivery

NCT03843788

Document Type: Statistical Analysis Plan

Document Date: 7/11/2024

Statistical Analysis Plan

All outcomes will be presented using descriptive statistics; normally distributed data by the mean and standard deviation (SD) and skewed distributions by the median and interquartile range (IQR).

Primary Outcome

The primary analysis will compare intervention groups (TENS vs usual care) on mean change in pain score as measured by Visual Analog Scale (VAS) over the course of the inpatient hospital stay. Measured primary outcomes were pain ratings, number and type of pain medications used, and patient satisfaction with pain control. Fixed effects repeated measures analysis of variance was used to evaluate the differences in pain scores between groups and Mann-Whitney tests were used to examine differences in medication intake. Additionally, repeated measures correlation (RMCORR) between TENS and usual care arms with an exploratory analysis of pain behavior in individuals with SUD compared to no SUD will be performed.

Secondary outcomes

Secondary outcomes will include pain surveys at 6 weeks postoperatively, time to first bowel movement, level of sedation, and time to out-of-bed (OOB).

Missing data

Mixed-effects procedure was utilized to avoid loss of data from missing values at different time points.

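### The first objective is opioid quantity, but no stated outcome measures it, maintenance opioid is not addressed, and the named test does not stratify by opioid history

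*Protocol*

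**What the plan says.** Protocol 1.1.A gives the first objective: "To determine if the addition of TENS therapy to the pain management of women post-C-Section leads to less opioid medication use". Protocol 1.2 puts the hypothesis in the same terms: women using TENS "will consume less opioid medication during the inpatient stay compared to women who do not utilize TENS after CS". Both are statements about quantity.

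Protocol 1.6.B names the medication outcome as "number and type of pain medications used". Protocol 4.11 lists the same item for chart abstraction, and the SAP repeats it under Primary Outcome: "Measured primary outcomes were pain ratings, number and type of pain medications used, and patient satisfaction with pain control". No section defines an opioid total, a common unit or a time window.

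The Data Collection paragraph of Protocol 1.3 does abstract "medication requests/prescriptions (including name, type, and amount", but no outcome or analysis refers back to the amount.

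Usual care in both arms includes opioids and NSAIDs (Protocol 1.3). Half the women form the opioid-history category, which Protocol 4.2.D defines as follows: "Opioid use will be obstetric patients on narcotic replacement with methadone or subutex". Protocol 1.3 and 1.5 set 5 TENS and 5 control women in each category.

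For the analysis, the SAP states that "Mann-Whitney tests were used to examine differences in medication intake". It does not mention category there. Its only analysis by opioid history is exploratory and concerns pain, not medication.

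**The concern.** Three things are left open, and each affects whether the trial can answer its first objective.

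- **Outcome.** The number of medications could mean distinct drugs, administrations or tablets. Under some of these meanings a real fall in opioid dose would not show. The term medication intake in the SAP is equally open, so the measure could be settled after the data are seen.
- **Maintenance opioid.** If methadone or Subutex were included, it would add opioid unrelated to incision pain to half of each arm.
- **Test.** Women with and without opioid history may differ widely in intake. A rank test that ignores category then spends its information on that difference and not on the arms.

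What is at stake is a null or uninterpretable opioid result from a pilot that Protocol 1.5 intends as the basis for larger trials.

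**Working it through.** **The plan's own figure.** There is no power calculation to reproduce (Protocol 6.1.B). The sample size is arithmetic only: 4 cells x 5 = 20, which agrees with Protocol 1.5 and 4.5.A. The 40 in Protocol 4.5.C is a separate discrepancy and is not used here.

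**Inputs from the documents.** 10 v 10 overall, 5 v 5 within each of two categories; Mann-Whitney test.

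**Inputs assumed.** Two-sided alpha 0.05 (none is stated); normal intake with SD 1 within category; TENS effect d; category gap g. The documents give no intake level, SD or gap, so a range is shown.

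**Check 1: an extreme case with no distributional assumption.** Suppose every TENS woman uses less than every control in her own category, and every opioid-history woman uses more than every woman without that history. The order from low to high is then 5 TENS, 5 control, 5 TENS, 5 control.

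- Unstratified: U is the number of TENS-control pairs in which the TENS woman uses more. Only the 5 TENS women with opioid history exceed any control, and they exceed the 5 controls without it, so U = 5 x 5 = 25. The exact two-sided p for 10 v 10 is 0.063.
- Stratified: each category has C(10,5) = 252 possible allocations, and this is the most extreme one in both. Two-sided p = 2/252² = 2/63,504 = 0.00003.

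**Check 2: power and size.** Model: intake = g x (opioid history) − d x (TENS) + N(0,1). Rejection regions from the exact null distributions:

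- Unstratified: U ≤ 23 or U ≥ 77, exact size 4.3% (U ≤ 24 would give 5.2%).
- Stratified: the sum of TENS ranks taken within category, W ≤ 41 or W ≥ 69, exact size 4.4%. This is the equal-weight van Elteren test.

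Simulated results (20,000 trials per setting):

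| Gap g (SD) | Size, unstratified | Power d = 1, unstratified | Power d = 1, stratified | Power d = 1.5, unstratified | Power d = 1.5, stratified |
|---|---|---|---|---|---|
| 0 | 4.2% | 51% | 49% | 86% | 83% |
| 1 | 2.4% | 41% | 50% | 77% | 83% |
| 2 | 0.4% | 18% | 50% | 52% | 83% |
| 3 | 0.0% | 4% | 49% | 20% | 83% |

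The stratified test keeps its size at about 4.4% throughout.

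**Check 3: maintenance doses, if they were counted.** Add between-woman variation of SD 3 in the opioid-history category only, with g = 3 and d = 1.5. Stratified power falls from 83% to 43%, and unstratified power is 21%. Stratifying does not remove this noise. Only the outcome definition does.

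**The case against.** Much of the strongest reading rests on silence.

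- A reader might infer that the outcome counts an NSAID the same as an opioid. The text does not support that. Type is recorded alongside number, so the classes can be separated. What is missing is a definition, and in particular any use of amount.
- A reader might infer that halving the opioid amount would go unseen. That holds only for some meanings of number. Protocol 1.1.B expects TENS to reduce requests for opioid, and a count of opioid administrations would then fall too.
- A reader might infer that maintenance methadone or Subutex is counted. No section says so. The Protocol calls these replacement medications, and the outcome is pain medications, so a plain reading may already leave them out. The point is that the text does not settle it.
- A reader might infer that the SAP commits to pooling the categories. It names Mann-Whitney tests in the plural and does not rule out tests by category.
- The power loss depends on the assumed gap. At 1 SD it is about 9 points, and the large losses need 2 to 3 SD. If maintenance doses are excluded, the gap, and with it the gain from stratifying, may shrink.
- This is an unpowered pilot, and Protocol 6.1.A names pain scores as primary. Power near 50% at a 1 SD effect, even after the change, shows that estimation matters more than the test.

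All of this limits the claim. It does not remove the mismatch: the objective is a quantity, the SAP lists medication use among its measured primary outcomes, and no outcome defines the quantity.

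**Conclusion.** The concern holds as a gap in specification. The objective and hypothesis are about opioid quantity, no stated outcome uses the amounts collected, the handling of maintenance methadone or Subutex is not stated, and the named test is not stratified by the categories built into the design.

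The documents do not support saying that an opioid-sparing effect will be hidden. They support saying that it can be. If the categories differ in intake, the unstratified test is conservative and loses power: at a 1 SD effect, from about 51% with no gap to 18% at 2 SD and 4% at 3 SD, against about 50% stratified. Its true size drops to about 0.4% and 0% at those gaps. With no gap, the two tests are about equal.

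These figures assume two-sided alpha 0.05, normal intake with equal SD, and exactly 5 v 5 per category. Protocol 4.3 describes no stratified randomization that would guarantee this split. The p-value of 0.063 in the extreme case needs only that split and non-overlapping categories.

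**What to change.** In the SAP, for the opioid objective:

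1. **Outcome.** Total inpatient opioid amount in oral morphine equivalents per 24 h, from hour 8 after cesarean (when TENS starts) to discharge, on the same clock in both arms. Use the amounts already abstracted and a conversion table fixed without reference to study arm.
2. **Maintenance opioid.** Exclude methadone and Subutex given as maintenance from this total and report them separately. Report NSAID amount separately as well. This is an outcome definition only and does not affect treatment.
3. **Analysis.** Make the stratified Hodges-Lehmann difference with 95% CI the main result, supported by an exact rank test stratified by opioid-history category (van Elteren).
4. **Description.** Keep number and type of medications as descriptive results.
5. **Status.** The SAP is dated 7/11/2024 and describes the tests in the past tense. If the data have already been analysed, label this analysis post hoc.

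The cost is SAP wording and a conversion step, with no new data. The downsides are that a conversion table must be chosen and that about 2 points of power are lost if the categories do not differ.

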### **1.7 Drugs/Devices/Biologics**

Device: FDA-approved TENS unit.

The TENS unit has four small adhesive patches which will be placed above and below the surgical incision site. The device will be set to a frequency between 100 and 120 Hz and utilize low-volt, pulsed current.

#### **A. Drug/Device Accountability and Storage Methods**

- *Indicate the specific location where study drugs/devices/biologicals will be stored and secured.*  
The device will be stored in a locked cabinet in [name] locked office.  
[name]  
[name]
- *Indicate who will be responsible for preparation, dispensing and disposal of study drug/device/biological.*  
The TENS device will be obtained and checked by [name]. It will be reevaluated with quality checks after each patient usage. New TENS pads will be provided for each patient. [name] will clean and sterilize the pads before application and as needed.

### **1.8 Primary Specimen Collection**

N/A

### **1.9 Interviews, Focus Groups, or Surveys**

#### **A. Administration**

Postoperative pain evaluation will be conducted using the survey tool, included as Appendix A. This will be provided by study staff

##### **▪ Timing and Frequency**

Survey will be performed at hospital discharge, as well as at 6 weeks postpartum.

Version Number: 5

Protocol Number: Pro2018001008

PI Name: [name]

Protocol Title: TENS after Cesarean Delivery

7

RESERVED FOR IRB STAMP

DO NOT MODIFY THIS SPACE

IRB ID: Pro2018001008

IRB Form Version: 01/2018

7/19/2022

Approval Date:

7/18/2023

Expiration Date:

7/18/2023

▪ **Location**

Surveys will be supplied to patient at bedside at discharge, and in the outpatient office during routine postpartum visit. However, if patients do not present for their routine 6 week postpartum visit, the final survey will be mailed to their last address of record, with a self-addressed stamped envelope to facilitate completion of study activities.

[figure not shown]
▪ **Procedures for Audio and Visual Recording**

N/A

**B. Study Instruments**

- Variables of interest for our study include perceptions of intensity and quality of postoperative pain. Two validated questionnaires will be used to achieve this objective as bulleted below. Additionally, basic questions about the acceptability of the TENS device in the post-cesarean setting, and intended vs. actual use are valuable for us to determine whether TENS is an acceptable modality for most women.
- The research questionnaire (Appendix A and B) will include 4 components:
  1. The McGill Pain Questionnaire, developed by [name] at McGill University
  2. The Neuropathic Pain Scale, developed by Drs. Galer and Jensen
  3. General questions about acceptability of the TENS unit in the postoperative setting.
  4. The WHO-DAS 2.0, developed by the World Health Organization, at the 6 week postpartum visit only (Appendix B).

## 2.2 Resources Available

**Facilities**-The postpartum maternity unit at Robert Wood Johnson Medical School provides high level care for women after Cesarean delivery.

**Medical Or Psychological Resources**- [name] will be available to provide medical oversight and answer patient questions during treatment.

**Research Staff Training**- [name] will be responsible for oversight and training of the team related to use of the TENS unit.

